In the “Adjustment Phase”, during the first 12 hours, sensor accuracy will be assessed. Patients will continue to have their blood glucose (BG) checked with POC glucometer concomitant with CGM use. Nursing staff will check POC BG every 1 hour for the first 12 hours (as per established IV insulin infusion protocol). CGM readings will be recorded in chart at the same time as POC glucometer reading is obtained. These readings will be entered by nursing staff under the “comments” section of the MAR screen. The glucometer readings and CGM data at the time of glucometer readings will be compared by nursing staff. The CGM readings should not be either 15% higher or 15% lower than the corresponding POC glucometer reading. Should this CGM reading fall outside this range, a second reading will be done within 30 minutes and readings will be compared to reassess accuracy. After the patient has had sensor in place for 12 hours and at least 12 POC glucometer glucose checks have been recorded and compared against CGM values, the research team will be notified to determine if the frequency of POC checks can be safely decreased based on CGM accuracy.

If 12 comparison points – CGM readings and POC glucometer reading – are deemed accurate (within +/- 15% of each other for all 12 readings), then patient will enter the “Utilization Phase”.

If 2 or more consecutive CGM readings do not correlate with POC glucometer values, the research team will be notified. The research team will evaluate the data and decide if the sensor should be replaced and another 12-hour cycle of adjustment phase re-initiated or if patient participation should be terminated.

Utilization Phase

Once CGM accuracy has been established in the “Adjustment Phase” above, the frequency of POC glucose checks will be reduced as follows:

1. POC glucometer checks will be reduced to every 2 hours
2. CGM readings will continue to be recorded hourly by nursing staff.
 - a. If CGM glucose remains in range (140-180 mg/dl), the same insulin infusion rate will be continued.
 - b. If CGM glucose is out of range (<140 or >180) then nursing staff will resume POC glucose check every 1 hour. Insulin infusion will be adjusted as needed per IV insulin infusion protocol using the POC glucometer reading **only**.
3. If IV insulin infusion dose is adjusted, nursing staff will resume POC glucometer checks every 1 hour until the POC glucose remains in range for 2 consecutive readings

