4. Once BG remains within range for 2 consecutive POC glucometer readings, POC glucose checks will be again decreased to every 2 hours

5. If the patient is transitioned from IV insulin infusion to SQ insulin, the nursing staff will notify the research staff and will proceed to the SQ insulin protocol above. The alarms will be adjusted as described in the SQ insulin protocol.

The CGM will be set up with alarm limits of **Low Glucose (<140 mg/dl)**, **Urgent Low Glucose (<70)** and **High Glucose (>180)**. If these alarms are triggered, the nursing staff will perform a STAT POC glucose check to confirm blood glucose (BG) level. Treatment decisions will be made based on the POC glucometer reading as follows:

- For hypoglycemia:
 - If POC BG is between 85-140 mg/dl, hold IV insulin infusion and re-check POC glucose in 30 minutes
 - If POC BG is between 70-84 mg/dl, hold IV insulin and ask patient to take 15gm of carbohydrates PO ASAP and recheck POC glucose level in 30 minutes
 - If POC BG is < 70, apply hypoglycemia protocol. Hold IV insulin. Give IV D50 or IM glucagon to obtunded patients. Give PO carbohydrates to alert, able to swallow patients. Repeat POC glucose level in 15 min. and 30 min.
 - Continue to check POC blood glucose every 1 hour until glucose remains in range (140-180 mg/dl) for 2 consecutive readings.
 - Once BG remains within range for 2 consecutive POC glucometer readings, POC glucose checks will be decreased to every 2 hours
- For hyperglycemia (BG>180):
 - Check glucose level using POC glucometer and adjust IV insulin infusion rate accordingly
 - Continue checking POC glucose every 1 hour until glucose remains in range (140-180 mg/dl) for 2 consecutive readings
 - Once BG remains within range for 2 consecutive POC glucometer readings, POC glucose checks will be decreased to every 2 hours

Methods (continued):

Treatment of the DM and associated complications, dosing of the insulin, change from PO to insulin treatment and back to PO medications during hospitalization or at discharge will be guided by the admitting team with as needed help from the inpatient Endocrinology Consultation Service.

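### IV insulin, CGM below 140 mg/dl: two unreconciled action lists apply, a POC of exactly 140 is both in range and in the hold band, and no end to a hold is stated while glucose stays at 140-180

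*Combined protocol and SAP*

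**What the plan says.** The IV insulin part of Study Design and Methods opens with a general rule that the infusion is adjusted on POC values only. Its Utilization Phase then gives numbered items:

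- Item 2a: "If CGM glucose remains in range (140-180 mg/dl), the same insulin infusion rate will be continued".
- Item 2b: "If CGM glucose is out of range (<140 or >180) then nursing staff will resume POC glucose check every 1 hour". It adds: "Insulin infusion will be adjusted as needed per IV insulin infusion protocol using the POC glucometer reading". The infusion protocol it names is not reproduced.
- Item 3 deals with a changed dose: "If IV insulin infusion dose is adjusted, nursing staff will resume POC glucometer checks every 1 hour until the POC glucose remains in range for" ... The exit it sets is two in-range readings in a row. Item 4 then returns checks to every 2 hours.

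After item 5, an alarm list sets a low alarm at CGM below 140, an urgent low alarm below 70 and a high alarm above 180. Its first step is "If these alarms are triggered, the nursing staff will perform a STAT POC glucose check to confirm blood glucose (BG) level", and its basis for action is "Treatment decisions will be made based on the POC glucometer reading as follows". The top low band reads "If POC BG is between 85-140 mg/dl, hold IV insulin infusion and re-check POC glucose in 30 minutes". The two lower bands (70-84 and below 70) also hold the infusion. All low bands then share one follow-up, "Continue to check POC blood glucose every 1 hour until glucose remains in range (140-180 mg/dl) for 2 consecutive readings", after which checks drop to every 2 hours. Above 180, the list calls for a POC check and a rate adjustment.

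Under Endpoints, POC frequency in the two phases is a primary endpoint, time in range is secondary, and DKA or HHS is a safety measure. Target accrual is 20.

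**The concern.** One state, CGM below 140 on IV insulin, falls under two lists that do not refer to each other. Item 2b leaves the infusion decision to an outside protocol. The alarm list fixes it as a hold when POC is in a hold band. The immediate POC check, the fixed hold and the 30-minute recheck appear only in the alarm list. A nurse therefore cannot tell from the page whether the alarm list spells out item 2b or replaces it.

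Two things are at stake. The first is patient safety: the written path runs from an infusion on hold to less frequent POC checks without stating how the hold ends. Type 1 diabetes is eligible, and DKA is both a discontinuation criterion and a safety measure. The second is measurement: POC frequency is a primary endpoint, and the number of checks in a low episode depends in part on which list is followed and how the 30-minute recheck is handled.

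**Working it through.** The plan gives no power calculation, expected check count or episode rate, so there is no figure to reproduce. The check compares the two lists and adds one illustrative count.

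**1. The two lists side by side**

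| | Item 2b, with items 3-4 | Alarm list |
|---|---|---|
| Trigger | CGM <140 (or >180) | CGM <140 (or <70, or >180) |
| First POC check | hourly checks resume; timing of the first not stated | immediate |
| Basis for infusion action | POC | POC |
| Action at POC 85-140 | as the infusion protocol requires | hold |
| Next check | 1 hour | 30 minutes |
| Checks after that | hourly | hourly |
| Exit | 2 consecutive in range, then 2-hourly | 2 consecutive in range, then 2-hourly |

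The lists agree on the basis for action, the hourly follow-up and the exit. They differ in the first check, the stated action and the 30-minute recheck.

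**2. The value 140**

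The hold band is 85-140 and the target range is 140-180. Their intersection is the single value 140. It can arise in practice. The low alarm needs CGM below 140, and the accuracy tolerance is ±15% of POC. At POC 140 the lower tolerance limit is 140 × 0.85 = 119, so a whole-number CGM reading of 119 to 139 sounds the low alarm and still counts as accurate. For example, CGM 125 is (140 − 125)/140 = 10.7% low. That POC reading calls for a hold and, being in range, also meets the criterion for stepping checks down.

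**3. Tracing a hold**

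- The POC value falls in a low band, and the infusion is held.
- Hourly checks continue until two consecutive readings lie in 140-180.
- Checks then drop to every 2 hours.
- Item 2a now applies and keeps the rate as it is. Read literally after a hold, that rate is zero.
- A rate adjustment is next prompted only above 180.

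While glucose stays at 140-180, no line in the items or the alarm list restarts the infusion.

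**4. POC checks in one low episode (illustrative)**

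Assumptions: POC starts at 85-139 and returns to range after T hours, with the same T under both lists. Checks are counted from the trigger to the second consecutive in-range reading, and the 30-minute recheck may count as one of the two. ⌈ ⌉ means round up.

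- Item 2b, first check at the trigger: ⌈T⌉ + 2.
- Alarm list, one 30-minute recheck then hourly: ⌈T − 0.5⌉ + 3, with the first term not below 0.
- Alarm list, recheck repeated every 30 minutes while POC stays in the hold band: ⌈2T⌉ + 2.

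| T (h) | Item 2b | Alarm, recheck once | Alarm, recheck repeated |
|---|---|---|---|
| 0.25 | 3 | 3 | 3 |
| 0.5 | 3 | 3 | 3 |
| 1 | 3 | 4 | 4 |
| 2 | 4 | 5 | 6 |
| 4 | 6 | 7 | 10 |

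Done once, the recheck adds 0 to 1 check. Repeated, it adds up to 10 − 6 = 4 at T = 4 h. If item 2b's first check comes at 1 hour, its counts fall by one and these differences become up to 2 and up to 5. If the 30-minute recheck may not count as one of the two readings, the recheck-once entries at T = 0.25 and 0.5 rise from 3 to 4 (checks at 0, 0.5, 1.5 and 2.5 h).

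**The case against.** The strongest reply is that no contradiction on the infusion has been shown. A hold is one form of adjustment, the unseen infusion protocol may itself require it at POC 85-140, and the alarm list can be read as the detail of item 2b. That stands. The two lists give different insulin only if that protocol says something else.

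Four stronger readings are tempting, and the documents do not support them:

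- A reader might infer that a CGM reading below 140 itself orders a hold. It does not. The alarm list requires a POC check first, and both lists act on POC.
- A reader might infer a choice between hourly checks and a 30-minute recheck, and so a doubled check rate. The alarm list has the recheck and then the same hourly checks. The two-fold ratio (60 against 30 minutes) describes one interval.
- A reader might infer that nothing ever ends a hold. Above 180 the alarm list calls for a rate adjustment. The gap is confined to 140-180.
- A reader might infer a demonstrated DKA risk. The documents give no figure for it.

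It is also fair to say that the Methods leave insulin dosing to the admitting team with endocrinology help as needed, that a separate IV flow-sheet will exist, and that administered medications are collected from the health record. These may fill the gaps in practice. The flow-sheet cannot be seen, however, and the text points to none of them as the rule for leaving a hold. None of this removes the overlap at 140 or the missing statement of precedence.

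**Conclusion.** The point holds in limited form. The two lists share a trigger with no stated precedence. Two inconsistencies stand on the page whatever the infusion protocol contains: POC 140 belongs to two bands, and a hold can lead to 2-hourly checks at an unchanged rate with no stated end while glucose stays at 140-180. If the infusion protocol does supply a restart rule, the text still does not say that it overrides item 2a.

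A difference in insulin exposure is possible but not proven, and it cannot be sized without that protocol. The effect on POC counts is about 0 to 1 extra check per low episode if the recheck is done once and item 2b starts at the trigger, and more if it is repeated. This rests on an assumed return to range in 0.25 to 4 hours, equal under both lists. The effect on the endpoint as a whole cannot be computed, because neither the number of IV patients among the 20 nor the number of episodes is given. The count effect is modest. The safety wording is the stronger reason to amend.

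**What to change.** Reconcile items 2a, 2b and 3 with the alarm list in a single IV action table with non-overlapping POC bands, so that each POC value leads to one infusion action and one recheck time. State in or beside the table:

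- which document governs, this protocol or the infusion protocol, including for leaving a hold;
- what an unchanged rate means after a hold;
- whether the 30-minute recheck is done once or repeated, and whether it counts toward the two consecutive readings and toward the POC-frequency endpoint.

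Record the start and end time of every hold, so that insulin-off periods can be identified in the analysis. The clinical content of the table is for the investigators to decide.

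The cost is one protocol amendment, a revised IV flow-sheet and re-briefing of nursing staff. No patients, visits or tests are added.

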**Outcomes measured:**

CGM accuracy when compared with POC monitors.

CGM accuracy at detection of hypo or hyperglycemia episodes when compared with POC monitors.

Number of CGM alarms and the clinical result of these alarms: nurse notification, treatment of hypo or hyperglycemia episodes, treatment for rapid declining glucose alarms.

Number of POC glucometer checks in the “Adjustment Phase” and in “Utilization Phase” will be recorded.

Hospital outcomes (length of stay, mortality, readmission and mortality at 30 days)

Patient satisfaction with DM management and inpatient care overall.

Criteria for Discontinuation of Individual Participants:

Subjects can decide to discontinue entirely from the study at any time for any reason. This is documented as withdrawal of consent. Subjects can also be discontinued from the study or discontinued from the study treatment due to Investigator decision as detailed below.

1. Withdrawal of consent.
2. At the Investigator’s discretion in certain situations such as lack of compliance or serious adverse event. (A single severe hypoglycemic event resulting in seizure or LOC or DKA).
3. 2 or more hypoglycemic events based on CGM readings that do not correlate with standard finger-stick blood glucose monitor readings and decision to remove the sensor.
4. One DKA event or one episode of hyperglycemic, hyperosmolar nonketotic syndrome (HHNS).
5. Skin infection at the site of device insertion that occurs after placement of the device.
6. Skin irritation at the site of device insertion prompting the patient to request removal of the device.
7. Transfer of the patient to the ICU with intubation, shock, placement on ECMO (Extracorporeal membrane oxygenation) or deterioration of medical condition that in the judgment of the principal investigator carries an unacceptable risk for the participant.

Materials:

CGMs (G6 sensors, G6 transmitters and Phone readers) provided and purchased from DEXCOM . iPad tablets provided by Mayo Clinic IT Department.

DEXCOM G6 app software is preinstalled on phone readers.

DEXCOM Follow app will be installed on iPads present at nursing station.

Personnel:

Diabetes educators and Endocrinology APRN will provide support for nursing staff and perform the tasks listed above.

Subject Information

Target accrual is the proposed total number of subjects to be included in this study at Mayo Clinic. A “Subject” may include medical records, images, or specimens generated at Mayo Clinic and/or received from external sources.

Target accrual: 20

Subject population (children, adults, groups):

Admitted adult patients with diabetes and hyperglycemia and diagnosed with COVID-19.

Inclusion Criteria:

Patients 18 years or older.

Patients with diagnosis of COVID-19 respiratory infection

Patient with recent positive SARS-COV2 infection and still positive PCR admitted of non-respiratory diagnoses.

Diagnosis of diabetes mellitus type 1 or type 2

Diagnosis of medication (steroid) induced hyperglycemia (persistent glucose more than 180 mg/dl)

Receiving subcutaneous insulin or IV insulin infusion for hyperglycemia (different protocols will be followed depending on type of insulin)

Exclusion Criteria:

Patients in shock

Patients intubated on mechanical ventilation

Patients with ESRD on HD

Patients placed on ECMO

Patients with DKA or HHS

Patients taking hydroxyurea

Patients receiving more than 4g of acetaminophen in 24 hours

Pregnant or nursing female patients

Patients with skin lesions at the application site that may interfere with placement of the sensor

Patients with known allergy to medical grade adhesive

Patients with significant edema which may interfere with finger stick sample

Patients receiving enteral or parenteral nutrition

Biospecimens

No biospecimens will be collected

Review of medical records, images, specimens

Check all that apply (data includes medical records, images, specimens).

Only data that exists before the IRB submission date will be collected.

Date Range for Specimens and/or Review of Medical Records:

Examples: 01/01/1999 through 12/31/2015, or all records through mm/dd/yyyy.

Note: The Date Range must include the period for collection of baseline data, as well as follow-up data, if applicable.

The study involves data that exist at the time of IRB submission **and** data that will be generated after IRB submission. Include this activity in the Methods section.

Examples

- The study plans to conduct a retrospective chart review and ask subjects to complete a questionnaire.
- The study plans to include subjects previously diagnosed with a specific disease and add newly diagnosed subjects in the future.

The study will use data that have been collected under another IRB protocol. Include in the Methods section and enter the IRB number from which the research material will be obtained. *When appropriate, note when subjects have provided consent for future use of their data and/or specimens as described in this protocol.*

Enter one IRB number per line, add more lines as needed

Data Specimens Data & Specimens _____

Data Specimens Data & Specimens _____

Data Specimens Data & Specimens _____

Data Analysis

Power Statement:

This a pilot study to demonstrate feasibility of CGM use in COVID patients and to determine if a subsequent more extensive implementation and studying of this device will be warranted.

Data Analysis Plan:

Data will be described as percentages or means. Pearson χ^2 and Kruskal Wallis tests will be used to compare categorical and continuous variables respectively. Odds ratios, 95% confidence intervals and p-values will be reported for each model. All tests of significance will be 2-sided and the level of statistical significance will be set at p-value < 0.05 .

Mean Absolute Relative Differences will be calculated between matched pairs of POC monitors and the closest CGM reading (within 5 minutes of POC). Additionally, level of agreement between the two devices will be examined with Bland-Altman plots, with particular attention focused on detection agreement in range (70-180 g/dl). Poisson or negative binomial regression will be utilized to assess count variables such as number of alarms, nurse notification, and hypo or hyperglycemia events adjusting for patient characteristics. Finally, longitudinal analysis will be conducted to determine differences associated with medications, clinical parameters or diagnosis. Analysis will seek to define if there are any differences between CGM and POC measurement based on these changes.

Endpoints

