During the first 24 hours, sensor accuracy will be assessed. Patients will continue to have their blood glucose checked with POC glucometer concomitant with CGM use. CGM readings will be recorded in chart at the same time as POC glucometer reading is obtained. The glucometer readings and CGM data at the time of glucometer readings will be compared by nursing staff. The CGM readings should not be either 15% higher or 15% lower than the corresponding POC glucometer reading. Should this CGM reading fall outside this range, a second reading will be done within 30 minutes and readings will be compared to reassess accuracy. After the patient has had sensor in place for 24 hours and at least 4 POC glucometer glucose checks have been recorded and compared against CGM values and found to fall within the above range, the research team will be notified to determine if the frequency of POC checks can be safely decreased based on CGM accuracy.

If 2 or more consecutive CGM readings do not correlate with POC glucometer values, the research team will be notified. The research team will evaluate the data and decide if the sensor should be replaced and another 24-hour cycle of adjustment phase re-initiated, or if patient participation should be terminated. Only POC glucometer readings will be used to make decision about insulin dosing and administration during this phase. When charting insulin

administration, nursing staff will manually enter the CGM readings obtained at the time of insulin administration into the chart under the “comments” on the MAR screen.

If 4 comparison points – CGM readings and POC glucometer reading – are deemed accurate (within +/- 15% of each other for all 4 readings), then patient will enter the “Utilization Phase”.

Utilization Phase

During this phase, once the research team has confirmed CGM accuracy, POC glucometer AND CGM readings will be used to make decisions about insulin dosing and administration. The use of POC glucometer will be decreased as follows:

1. POC glucometer checks will be reduced from 4 times per day (qAC and QHS) to twice per day before breakfast and at bedtime (qAM and qHS)
2. Subcutaneous insulin dose for breakfast and bedtime will be determined based on POC readings
3. Subcutaneous insulin dose for lunch and dinner will be determined based on CGM readings
4. Nursing staff will continue to record CGM readings at the time of every insulin administration in the chart under the “comments” section on the MAR

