**Primary:**

CGM accuracy - mean absolute relative difference (MARD)

The frequency of POC glucometer use in Adjustment and Utilization phase

Secondary:

- CGM accuracy at detection of hypo or hyperglycemia episodes when compared with POC monitors. (MARD for readings <70g/dl, >180g/dl, >250g/dl)
- CGM accuracy for detecting time in range (70-180 g/dl MARD).
- Number of CGM alarms and the clinical result of these alarms: nurse notification, treatment of hypo or hyperglycemia episodes, treatment for rapid declining glucose alarms.
- Time in therapeutic range for glucose as measured by CGM and POC glucose monitor.
- Detection of medications, clinical parameters or diagnoses that would interfere with CGM reading.
- Effect of CGM use on length of hospital stay.

Clinical safety measures:

- Patients with severe hypoglycemia episodes (POC glucose check below 50 mg/dl).
- Patients with DKA or HHS diagnoses after admission and enrollment in the study.
- Number of sensors with failure.
- Number of sensors removed for procedure.
- Number of sensor related skin reaction (contact dermatitis, infection)

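### The plan makes no allowance for repeated CGM-POC pairs per patient in any interval for MARD or agreement, and names no within-patient method for the primary comparison of POC frequency between phases

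*Combined protocol and SAP*

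**What the plan says.** The Endpoints section lists two primary endpoints: MARD, and "The frequency of POC glucometer use in Adjustment and Utilization phase".

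For accuracy, the Data Analysis Plan says that "Mean Absolute Relative Differences will be calculated between matched pairs of POC monitors and the closest CGM reading", with a 5-minute window, and that "level of agreement between the two devices will be examined with Bland-Altman plots". The matched pair is therefore in effect the unit of analysis. Target accrual is 20 (Subject Information). On subcutaneous (SQ) insulin the Adjustment Phase runs until "at least 4 POC glucometer glucose checks have been recorded and compared against CGM values"; on IV insulin the corresponding number is 12. Retests within 30 minutes and the paired checks of the Utilization Phase add to this.

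For comparisons, the plan says that Pearson chi-square and "Kruskal Wallis tests will be used to compare categorical and continuous variables respectively". For counts, "Poisson or negative binomial regression will be utilized to assess count variables such as number of alarms", nurse notifications and glycemic events, adjusted for patient characteristics. It adds: "Odds ratios, 95% confidence intervals and p-values will be reported for each model". No patient term, robust variance, time offset or weighting rule appears.

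One sentence does touch repeated data. It plans a longitudinal analysis of whether medications, clinical parameters or diagnoses alter the CGM-POC difference, and names no model.

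**The concern.** Pairs from one patient share a sensor, an insertion site and a clinical state, so their errors are likely to be correlated. An interval that counts every pair as independent claims more information than 20 patients hold. The Power Statement says the pilot is "to determine if a subsequent more extensive implementation and studying of this device will be warranted", and that judgement depends on how precisely accuracy is known.

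The phase endpoint has the reverse structure. Each patient who reaches Utilization is their own control, and the baseline check rate differs sixfold between routes (24 v 4 per day). An independent-sample test leaves that between-patient spread in the noise. An unclustered count model without an offset ignores both the pairing and the unequal phase lengths. Only patients who pass the 15% accuracy gate have both phases, and the plan does not say how the others are reported.

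**Working it through.** The plan states no precision or power figure, so there is none to reproduce.

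**Inputs from the documents.** 20 patients. SQ pairs by day d: 4 + 2(d − 1), so 12 pairs at day 5 and 20 at day 9. IV pairs: 12 in 12 hours, then one every 2 hours, so 20 at 12 + 8 × 2 = 28 hours.

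**Assumed inputs.** Normal relative errors with total variance 136, an SD of 11.7 points (for example a patient-bias SD of 6 and a within-patient SD of 10, giving ICC = 36/136 = 0.26). ICC range 0.10 to 0.44. True MARD = √(2/π) × 11.66 = 9.3.

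**Mean bias.** Design effect D = 1 + (m − 1) × ICC. Coverage of a pooled 95% interval = 2Φ(1.96/√D) − 1. With m = 20 and ICC = 0.44: D = 1 + 19 × 0.44 = 9.36, 1.96/√9.36 = 0.64, coverage about 48% (47% simulated).

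**MARD.** Absolute errors are less correlated than signed errors. For normal errors with correlation r, the correlation of absolute errors is (2/π)[r·arcsin r + √(1 − r²) − 1]/(1 − 2/π): 0.009, 0.060 and 0.173 for r = 0.10, 0.26 and 0.44. With m = 20 and r = 0.44: D = 1 + 19 × 0.1725 = 4.28, coverage 66%.

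Simulated coverage (6,000 replicates), which the formulas match to about one point:

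| ICC | MARD, 4 / 12 / 20 pairs | Mean bias, 4 / 12 / 20 pairs |
|---|---|---|
| 0.10 | 95 / 94 / 93% | 91 / 82 / 76% |
| 0.26 | 92 / 87 / 81% | 85 / 68 / 58% |
| 0.44 | 88 / 75 / 66% | 80 / 58 / 47% |

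Patient-level t intervals on 19 df covered 93–95% (MARD) and 95% (bias). The limits of agreement themselves shrink by only 0.3–1.4%, but a pooled interval around the upper limit covers 93% down to 56%.

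**Unequal pair counts.** With an assumed 5 IV × 12 and 15 SQ × 4, five patients supply 60 of 120 pairs. Σm²/Σm = 960/120 = 8, so D = 1 + 7 × ICC. Simulated coverage at the three ICCs is 94/89/80% for MARD and 87/75/67% for bias.

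**Phase endpoint: rates and offset.** Take an SQ patient with one day of Adjustment (4 checks) and, as an assumption, four days of Utilization (4 × 2 = 8 checks). The raw count ratio is 8/4 = 2, while the daily rate ratio is 2/4 = 0.5. Without an offset the direction reverses. For a patient on IV in Adjustment (24 per day) and on SQ in Utilization (2 per day) the ratio is 2/24 = 0.08, of which 4/24 = 0.17 comes from the change of route alone.

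**Phase endpoint: tests.** Assumed 24 and 4 checks per day at baseline, SD 4 and 1, independent phases, 3,000 replicates. Power, Kruskal-Wallis v signed-rank on log rates:

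| Patients | 20% cut (assumed) | 50% cut (scheduled) |
|---|---|---|
| 5 IV + 15 SQ | 23% v 71% | over 99% for both |
| 3 IV + 13 SQ | 23% v 57% | 98% v over 99% |
| 1 IV + 7 SQ | 13% v 27% | 80% v 90% |
| 20 SQ | 68% v 64% | no loss |

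Kruskal-Wallis type I error is 0.2% with 5 IV + 15 SQ and 5% with SQ only.

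**Gate.** With bias SD 6 and within-patient SD 10, an all-pairs 15-point gate passes 44% of SQ and 10% of IV patients without a retest, or 84% and 63% with one. From 15 SQ + 5 IV, that is 15 × 0.44 + 5 × 0.10 = 7.1, or 15 × 0.84 + 5 × 0.63 = 15.7 patients with both phases, before any sensor replacement.

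**The case against.** The strongest reply is that the plan does not contain the faulty interval. MARD is only to be calculated and agreement plotted; intervals are promised for models, and neither is a model. This stands. A reader might infer that the plan commits to a pooled interval, or that MARD and the agreement limits will be wrong. The documents support neither reading. The gap is that no interval method is given, and no named method would account for clustering.

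A reader might also infer that repeated measurement is ignored throughout. The longitudinal-analysis sentence rules that out. But it names no model and concerns interfering factors, so it does not reach overall MARD, the agreement limits or POC frequency.

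POC checks are a count, and the count-model list is open-ended, so Kruskal-Wallis may never be applied to them. This stands too: the power figures are conditional. The count models as described still have no patient term or offset. The schedule halves checks by design, and at that cut the choice of test matters little.

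Finally, the absolute effect on MARD is modest. The simulated half-width, pooled v patient-level, is 1.53 v 1.64 points with 4 pairs and ICC 0.10, and 0.68 v 1.47 with 20 pairs and ICC 0.44. At the low end the difference is essentially t on 19 df in place of z. Mean bias, where coverage falls furthest, is not a listed endpoint. With no MARD threshold or go/no-go rule, no formal decision turns on these intervals. That limits severity but does not remove the point.

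**Conclusion.** The point holds as a gap in the specification, of minor to moderate severity for a 20-patient pilot. If a pooled 95% interval is reported, its coverage would be about 95% down to 66% for MARD and 91% down to 47% for mean bias over the assumed ICCs and pair counts. The effect on MARD is negligible with few pairs and low ICC. The documents give no ICC, error SD, route mix or length of stay, so all these figures are illustrative.

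For the phase endpoint, none of the named methods fits a within-patient contrast. The stronger inference, that the comparison is badly underpowered, is not supported: a large loss needs Kruskal-Wallis, a partial cut and mixed routes together. It is small or nil at the scheduled 50% cut or with SQ patients only.

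The promise of odds ratios for each model is a small wording error, since the only regressions named by type, Poisson and negative binomial, give rate ratios.

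**What to change.** - **MARD and mean bias.** Report patient-clustered intervals: patient-level t, or cluster-robust standard errors with patients minus 1 df. State pair or patient weighting and whether retest pairs count, and report by insulin route.
- **Agreement.** Use repeated-measures Bland-Altman limits (between- plus within-patient variance), with patient-clustered intervals.
- **POC frequency.** Model checks by Poisson or negative binomial regression with a patient effect (or cluster-robust standard errors), a log time-in-phase offset, and insulin route as a time-varying covariate, because patients may move from IV to SQ during the study. Alternatively, use a paired test on patient-level daily rates, restricted to patients on the same route in both phases. Label the result as applying to patients who passed the 15% gate, and report how many never entered Utilization. With 5 or fewer IV patients the exact two-sided signed-rank p-value cannot fall below 2/2⁵ = 0.0625, so describe IV results rather than test them alone.
- **Count models.** Report rate ratios.

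The cost is SAP wording and some programming, with no new data. The downsides are wider intervals (MARD half-width about 1.07 to 2.16 times the pooled one in the equal-pair scenarios above), a changed estimand if MARD is patient-weighted, and a phase comparison confined to gated patients.
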